## **6.3. Secondary Efficacy Endpoints**

### **6.3.1. Definition of Secondary Efficacy Endpoints**

The secondary efficacy endpoints include the following:

- Proportion of subjects establishing combined fistula remission at Week 24
- Time to clinical fistula response
- Time to clinical fistula remission
- Proportion of subjects achieving proctitis remission at Week 24, in subjects that had moderately to severely active proctitis at baseline

Please refer to [Table 6-1](#) for the definitions of the endpoints.

### 6.3.2. Analysis of the Secondary Efficacy Endpoints

For binary endpoints, the same statistical analysis method for analyzing the primary efficacy endpoint will be utilized.

If the proctitis SES-CD score is missing at Week 24, no imputation will be done and the subject will be considered a non-responder when deriving the proportion of subjects achieving proctitis remission at Week 24.

For time-to-event secondary efficacy endpoints, the summary statistics (eg, median, Q1, Q3) from the Kaplan-Meier method will be provided for each treatment group. Plot of Kaplan-Meier curves will also be provided. The Cox proportional hazards model will be used to estimate the hazard ratio with the corresponding 90% CI. Subjects not known to have a clinical fistula response (or remission) will have their clinical fistula response (or remission) time censored at the last perianal fistula assessment date.

No formal hypothesis testing will be performed.

CCI

CCI

[figure not shown]
CCI

CCI

CCI

CCI

CCI

CCI

The figure consists of a 10x10 grid of black bars on a white background. The bars are arranged in a pattern where most are horizontal, with some vertical and diagonal variations. The bars are of varying lengths, creating a stepped effect. The grid is bounded by a thick black border.

CCI

CCI

■

■

■

■

■

■

■

■

■

■

■

■

■

■

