3.4. Duration of Treatment

Randomized subjects will receive a maximum of 24 weeks of study drug. Subjects who are non-responders based on the results of the Week 10 assessments (see Section 3.6 OR Section 3.7 or meeting disease worsening criteria after Week 10 (see Section 3.8) must be discontinued from blinded treatment (see Section 3.5.2).

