**Table 1-1. Combined Fistula Response Rates (90% CI)**

Number Randomized	Number of Responders	Response rate	Lower Limit of 90% CI	Upper Limit of 90% CI
30	6	20%	9%	36%
30	9	30%	17%	47%
30	12	40%	25%	57%
30	15	50%	34%	66%
30	18	60%	43%	75%
30	21	70%	53%	83%
30	24	80%	64%	91%

CI = confidence interval

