**Table 6-1. Definitions of Selected Efficacy Endpoints**

Type	Endpoint	Definition
Primary	Combined fistula response at Week 24	Reduction of $\geq 1$ from baseline in the number of draining external perianal fistula openings that were present at baseline, and absence of fluid collections $> 1\text{cm}$ on MRI pelvis at Week 24, among subjects with at least 1 draining external perianal fistula opening at baseline
Secondary	Combined fistula remission at Week 24	Perianal fistula closure of all external openings that were draining at baseline, and absence of fluid collections $> 1\text{cm}$ on MRI pelvis at Week 24, among subjects with at least 1 draining external perianal fistula opening at baseline
Secondary	Time to clinical fistula response	The time interval in days from date of first dosing of study drug to the first observation (during scheduled or unscheduled clinical visits) when $\geq 1$ of the draining external perianal fistula openings that were present at baseline achieves perianal fistula closure, among subjects with at least 1 draining external perianal fistula opening at baseline. Subjects not known to have a clinical fistula response will have their clinical fistula response time censored at the last time that lack of clinical fistula response was documented.

Type	Endpoint	Definition
Secondary	Time to clinical fistula remission	The time interval in days from date of first dosing of study drug to the first observation (during scheduled or unscheduled clinical visits) of perianal fistula closure of all external openings that were draining at baseline, among subjects with at least 1 draining external perianal fistula opening at baseline. Subjects not known to have a clinical fistula remission will have their clinical fistula remission time censored at the last time that lack of clinical fistula remission was documented.
Secondary	Proctitis remission at Week 24, in subjects that had moderately to severely active proctitis at baseline	A Proctitis SES-CD Score (sum of ulcer size and ulcerated surface SES-CD endoscopy subscores for the rectum and anal canal) of 0 assessed by centrally read flexible sigmoidoscopy at Week 24, in subjects that had moderately to severely active proctitis at baseline
		CCI
		CCI

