#### **Non-responder Imputation**

For analysis of binary efficacy endpoints defined in [Table 6-1](#), subjects who do not have sufficient measurements due to any reason (including treatment failures and CDAI or PDAI non-responders at Week 10) to determine the endpoint will be considered not meeting the endpoint (ie, non-responder imputation [NRI]).

CCI

CCI

CCI

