## **Appendix 11. Study Treatment Failure Rules for Perianal Fistulizing CD Activity Related Efficacy Endpoints**

Study treatment failure rules described in this appendix apply to treatment failure that occurs during the course of the study, and will be applied to all the following efficacy endpoints related to perianal fistulizing CD activity:

- Proportion of subjects establishing combined fistula response at Week 24
- Proportion of subjects establishing combined fistula remission at Week 24
- Time to clinical fistula response
- Time to clinical fistula remission

All related efficacy data will be censored (set to missing) after treatment failure criteria are met, regardless of the observed data. Subjects who do not have sufficient measurements after censoring to determine the dichotomized endpoint(s) will be considered non-responder for corresponding endpoint (s). Study treatment failure rules override other data handling rules.

Subjects who have any of the following events will be considered a study treatment failure after the earliest event through the end of the study, regardless of the actual efficacy data collected.

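### Time to clinical fistula response and remission: efficacy-driven exits are censored, so 1 minus Kaplan-Meier can exceed the share who respond without prior failure; add a supplementary cumulative incidence

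*SAP*

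**What the plan says.** SAP 6.3.2 plans Kaplan-Meier quartiles and curves per arm and a Cox hazard ratio with a 90% CI, without hypothesis testing. Subjects with no known event "will have their clinical fistula response (or remission) time censored at the last perianal fistula assessment date". For response, SAP Table 6-1 puts it as "censored at the last time that lack of clinical fistula response was documented", and it has the matching rule for remission. Neither place distinguishes reasons for leaving.

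SAP Appendix 11 names both time-to-event endpoints. Efficacy data after a failure criterion is met are set to missing, and "Study treatment failure rules override other data handling rules". Such a subject is "considered a study treatment failure after the earliest event through the end of the study, regardless of the actual efficacy data collected". A subject who fails before any response is therefore censored at the last assessment before failure.

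Week 10 non-responders and subjects whose disease worsens after Week 10 "must be discontinued from blinded treatment" (Protocol 3.4; also 3.8). The perianal criterion in Protocol 3.7 is a higher PDAI discharge or pain subscore than at baseline at both Week 6 and Week 10. The luminal criteria in 3.6 and 3.8 use the CDAI.

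The SAP's non-responder imputation is introduced with "For analysis of binary efficacy endpoints". It counts treatment failures and CDAI or PDAI non-responders who lack sufficient measurements as not meeting the endpoint.

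**The concern.** Kaplan-Meier treats a censored subject as someone who would go on to respond at the same rate as those still under observation. That is hard to defend for a subject removed because fistula discharge had worsened, since the endpoint is cessation of drainage. The link is weaker for subjects who leave on the CDAI alone.

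Two of the four secondary efficacy endpoints are involved. The study is descriptive, so curves and quartiles carry much of their message. A reader may take the height of 1-KM at Week 24 as the share of the arm that responded. It is not that share once efficacy-driven exits are censored, and the discrepancy can differ between arms. The same subjects count as failures in the binary endpoints, so the two sets of results will not line up and the visible text does not explain why.

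**Working it through.** **The plan's own figure.** The only precision calculation in the documents is SAP Table 1-1. For 15/30, the Clopper-Pearson 90% limits from beta quantiles are 33.89% and 66.11%, which round to the printed 34% and 66%. All seven rows reproduce. This is the yardstick for sampling error below.

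**Inputs.** Arm sizes of 30 and 15 are from SAP 1.3. Visit days 15, 29, 43, 71, 99, 127 and 169 are from the schedule of assessments. All response and exit counts are assumptions, because the documents give none.

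**Formulas.** With r_k responses among n_k at risk at visit k:
- 1-KM = 1 − ∏(1 − r_k/n_k), with leavers removed from n_k.
- Cumulative incidence (Aalen-Johansen, AJ) = Σ S(t_k−)·r_k/n_k, where S falls at responses and at failures.

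Each later response is weighted by KM survival in the first and by the smaller overall event-free probability in the second. So 1-KM is larger whenever a response follows an exit, and equal otherwise. In 40,000 random data sets on the perianal assessment visits, 1-KM was larger in all 39,402 with a response after an exit and equal in the other 598.

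If all e exits occur at Week 10 and a fraction l of the stayers respond later, the gap is (e/n)·l. KM credits each leaver with probability l of responding; AJ credits none.

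**Few exits.**
- Active: 8 responses by Day 71, 2 exits, 7 later responses. 1-KM = 1 − (22/30)(13/20) = 52.3%; AJ = 15/30 = 50.0%.
- Placebo: 3 responses by Day 71, 1 exit, 3 later responses. 1-KM = 1 − (12/15)(8/11) = 41.8%; AJ = 6/15 = 40.0%.

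**More exits.**
- Active: 8 responses, 5 exits, then 2, 2 and 2 responses at Days 99, 127 and 169. 1-KM = 1 − (22/30)(11/17) = 52.5%; AJ = 14/30 = 46.7%. Gap 5.9 points.
- Placebo: 3 responses, 5 exits, 2 later responses. 1-KM = 1 − (12/15)(5/7) = 42.9%; AJ = 5/15 = 33.3%. Gap 9.5 points.
- Active 1-KM is 43.9% at Day 127 and 52.5% at Day 169, so the KM median is Day 169. AJ never reaches 50%. Q1 (Day 71 active, Day 99 placebo) and Q3 (not reached) agree under both.

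**Other patterns, n = 30.**
- Adding unrelated exits (8 responses, then 5 failures and 4 unrelated exits at Week 10, then 5 responses): 1-KM = 1 − (22/30)(8/13) = 54.9%; AJ = 8/30 + (17/30)(5/13) = 48.5%.
- Failures spread over time (responses 1, 2, 2, 3, 2, 2, 2 at the seven visits; failures 1, 3, 1, 1 at Days 43, 71, 99, 127; 1 unrelated exit at Day 71): 54.9% against 47.8%.

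**Unequal exits.** Let AJ be 40% in both arms, with half of the responses before Week 10. With 3/30 active exits, 1-KM = 1 − (24/30)(15/21) = 42.9%. With 6/15 placebo exits, 1-KM = 1 − (12/15)(3/6) = 60.0%.

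**The no-exit probability.** Suppose leavers in the more-exits case would have responded at half the stayers' rate. The values without exits are (14 + 5·0.5·6/17)/30 = 49.6% and (5 + 5·0.5·2/7)/15 = 38.1%. KM is 2.9 and 4.8 points too high. AJ is too low by the same amounts, because it estimates something else.

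**The case against.** The stated objective is to assess time to response, not the share responding by Week 24, and censoring at exit is a recognised approach to a hypothetical question. That stands as a defence of keeping Kaplan-Meier, which the protocol specifies (Synopsis and 8.5.2). However, the visible SAP does not state that aim, and KM meets it only if leavers would have responded at the stayers' rate.

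Every rate above is assumed, and the median changed because the chosen counts straddle 50%. Both points stand.

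Some leavers are also seen again. A perianal assessment is scheduled at early termination (Protocol 6.14) and, for those not entering the extension study, 30 days after the last dose (6.13). Such a subject can stay at risk beyond Day 71 or be recorded as responding, whereas the calculations remove every leaver at the assumed exit visit. Counting CDAI-only exits as failures of a fistula endpoint is debatable too, since Appendix 11 has no CDAI criterion.

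Disposition tables (SAP 4.1) and reasons for not meeting the binary endpoints (SAP 6.1) will show exits by arm. They help the reader but do not correct the curves.

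Four stronger readings are tempting and are not supported:
- *The SAP contradicts itself.* Non-responder imputation is confined to binary endpoints, so the handling differs without a textual conflict.
- *Kaplan-Meier is wrong and should be replaced.* It is protocol-specified, and cumulative incidence does not estimate the no-exit probability either.
- *The method favours filgotinib.* With more exits, the arm difference is 9.6 points under KM (52.5 − 42.9) and 13.3 under AJ (46.7 − 33.3, before rounding). In the unequal-exits case KM favours placebo.
- *No competing-risk analysis is planned.* Much of the text after 6.3.2 is redacted, so this cannot be known.

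**Conclusion.** The point holds as a matter of interpretation and a missing supplementary estimate. Under the visible rules, 1-KM exceeds the probability of responding without prior failure whenever a response follows an efficacy-driven exit in that arm. The gap grows with the share who exit and with the later response rate among stayers; for similar response patterns it is larger in the arm with more exits.

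Under the Week 10 exit counts assumed, it is about 2 points with 2/30 and 1/15 exits and about 6 and 10 points with 5/30 and 5/15. This is smaller than the sampling error: SAP Table 1-1 runs from 34% to 66% for 15/30, or 16 points either side. Unlike sampling error, though, the gap has a known direction and can differ by arm. A median near 50% may be reported as reached when the cumulative incidence does not reach 50%; quantiles reached by Week 10 are not changed by Week 10 exits.

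The Cox hazard ratio remains valid as a cause-specific hazard ratio. The primary endpoint and the sample size are untouched. The change should be made, but confidence is medium because the rates are unknown and part of the SAP cannot be read.

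**What to change.** Keep the Kaplan-Meier and Cox analyses and label the hazard ratio cause-specific. Add to SAP 6.3.2, for both endpoints:
- A supplementary Aalen-Johansen cumulative incidence per arm. Competing events, when they precede the response or remission, are Appendix 11 treatment failure and study exit for Week 10 non-response or disease worsening. A response or remission first seen at the same visit counts as the event. Other exits are censored at the last assessment.
- The same display with CDAI-only exits censored.
- A listing of any response or remission recorded after exit, for example at the post-treatment visit.
- A statement that 1-KM is not the share of subjects who respond by Week 24.

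The cost is SAP wording, one derived failure date and the extra displays for each endpoint; no new data are needed. The added curves will lie below the Kaplan-Meier curves wherever a response follows a competing event, and they describe response without prior failure, which must be stated beside them. If the redacted text already holds such an analysis, only the labelling and any missing pieces are needed.

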## 7. SAFETY ANALYSES

Unless otherwise specified, summaries of safety data will be provided for the Safety Analysis Set and will include data collected up to the last dose of study drug plus 30 days.

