6.13. Post-Treatment Assessments

All subjects must complete the PTx assessments 30 days after the last dose of study drug. Only subjects who choose to participate in the LTE study will not complete PTx assessments associated with this protocol:

- Symptom-directed PE including perianal assessment
- Obtain body weight and vital signs (resting blood pressure, respiratory rate, pulse, and temperature)
- Review AEs and concomitant medications
- Obtain blood samples (see Study Procedures Table [[Appendix 2](#)])
- Obtain urine sample for pregnancy test (for females of childbearing potential only)

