8.6. Safety Analysis

Safety will be evaluated by assessment of clinical laboratory tests, PE, ECG and vital signs measurements at various time points during the study, and by the documentation of AEs. All safety data collected on or after the first dose of study drug administration (Day 1) up to 30 days after permanent discontinuation of study drug will be summarized by treatment group according to the study drug received.

All data collected during the course of the study will be included in data listings.

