Appendix 2. Study Procedures Table

Period	Screening	Treatment										Follow-Up	
		1	2	3	4	5	6	7	8	9	10	PTx ^a	ET
Visit	1	0	2	4	6	10	14	18	20	24			
Week													
Study Day	-30 to -1	1	15	29	43	71	99	127	141	169			
Visit Window (±)			±3	±3	±3	±2	±3	±3	±5	±5	±3		
Written Informed Consent	X												
Medical History & Demographics	X												
Crohn's Disease & Treatment History	X												
12-lead ECG	X					X							X ^b
Review of Inclusion/Exclusion Criteria	X	X											
Physical Exam (Complete including perianal) ^c	X												
Physical Exam (symptom-based) and perianal assessment ^c		X	X	X	X	X	X	X		X	X	X	
Vital Signs	X	X	X	X	X	X	X	X		X	X	X	
Weight	X	X	X	X	X	X	X	X		X	X	X	
Height	X												
Adverse Events	X	X	X	X	X	X	X	X		X	X	X	
Concomitant Medications	X	X	X	X	X	X	X	X		X	X	X	
Randomization		X											
Study Drug Dispensing		X		X		X	X	X					
CCI													
CCI													
eDiary instruction & review ^e	X	X	X	X	X	X	X	X		X			
Flexible Sigmoidoscopy ^o	X									X			X ^r
MRI ^f	X									X			X ^s

Period	Screening	Treatment									Follow-Up		
		1	2	3	4	5	6	7	8	9	10	PTx ^a	ET
Visit													
Week			0	2	4	6	10	14	18	20	24		
Study Day	-30 to -1	1	15	29	43	71	99	127	141	169			
Visit Window (±)			±3	±3	±3	±2	±3	±3	±5	±5	±3		
Stool for C. diff toxin, pathogenic E. coli , Salmonella , Shigella , Campylobacter and Yersinia testing	X												
Stool O&P	X												
CCI													
Fecal Lactoferrin, Calprotectin	X										X		
Urine drug screen ^g	X												
Urinalysis ^q	X										X		
Pregnancy Test ^h	X	X		X	X	X	X	X	X	X	X	X	
TB screening ⁱ	X												
Chest x-ray ^q	X												
HBV, HCV, HIV screening ^j	X												
Hematology	X	X	X	X	X	X	X	X		X	X	X	
Chemistry	X	X	X	X	X	X	X	X		X	X	X	
Fasting Lipids ^p		X				X					X		
CRP	X	X	X	X	X	X	X	X		X	X	X	
Blood TCR/BCR repertoire sample ^k		X		X		X					X		
Plasma biomarker sample		X		X		X					X		
Serum biomarker sample		X		X		X					X		
Blood transcriptome sample		X		X		X					X		
CCI													
Serum immunoglobulin		X		X		X				X	X	X	
CCI													

Period	Screening	Treatment									Follow-Up	
Visit	1	2	3	4	5	6	7	8	9	10	PTx ^a	ET
Week		0	2	4	6	10	14	18	20	24		
Study Day	-30 to -1	1	15	29	43	71	99	127	141	169		
Visit Window (±)			±3	±3	±3	±2	±3	±3	±5	±5	±3	

CCI
CCI

a The Post-Treatment (PTx) visit should occur 30 days after the last dose of study drug. Only subjects who roll over into the LTE study will not complete PTx assessments.

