#### 7.1.5. Treatment-Emergent Adverse Events

##### 7.1.5.1. Definition of Treatment-Emergent Adverse Events

Treatment-emergent adverse events (TEAEs) are defined as 1 or both of the following:

- Any AEs with an onset date on or after the study drug start date (Day 1) and no later than 30 days after permanent discontinuation of study drug
- Any AEs leading to premature discontinuation of study drug.

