#### 7.2. Laboratory Evaluations

Laboratory data collected during the study will be analyzed and summarized using both quantitative and qualitative methods. Summaries of laboratory data will be provided for the Safety Analysis Set for data collected up to the last dose of study drug plus 30 days for subjects who have permanently discontinued study drug.

The analysis will be based on values reported in conventional units. When values are below the LOQ, they will be listed as such, and the closest imputed value will be used for the purpose of calculating summary statistics as specified in Section 3.6. Test results from hemolyzed samples will not be included in the analysis, but they will be listed in by-subject laboratory listings.

A by-subject listing for laboratory test results will be provided by subject ID number and time point in chronological order for hematology, serum chemistry, urinalysis, lipid profile, and serum immunoglobulin separately. Values falling outside of the relevant reference range and/or having a severity grade of 1 or higher on the Common Terminology Criteria for Adverse Events (CTCAE) severity grade will be flagged in the data listings, as appropriate.

Hematocrit collected from local laboratories due to COVID-19 impact will not be included in the safety laboratory summary, but they will be included in the listing with a flag to indicate which records were collected at a local laboratory.

No formal statistical testing is planned.

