### 7.2.2.1. **Treatment-Emergent Laboratory Abnormalities**

Treatment-emergent laboratory abnormalities are defined as values that increase at least 1 toxicity grade from baseline at any postbaseline time point, up to and including the date of last dose of study drug plus 30 days for subjects who permanently discontinued study drug.

If the relevant baseline laboratory value is missing, any abnormality of at least Grade 1 observed within the time frame specified above will be considered treatment emergent.

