### 7.2.2.3. **Summaries of Laboratory Abnormalities**

Laboratory data that are categorical will be summarized using the number and percentage of subjects in the study with the given response at baseline and each scheduled postbaseline time point.

The following summaries (number and percentage of subjects) for treatment-emergent laboratory abnormalities will be provided by lab test and treatment group; subjects will be categorized according to the most severe postbaseline abnormality grade for a given laboratory test:

- Graded laboratory abnormalities
- Grade 3 or higher laboratory abnormalities
- Marked laboratory abnormalities

For all summaries of laboratory abnormalities, the denominator is the number of subjects with nonmissing postbaseline values up to 30 days after last dosing date.

A by-subject listing of treatment-emergent Grade 3 or 4 laboratory abnormalities will be provided by subject ID number and time point in chronological order. This listing will include all test results that were collected throughout the study for the lab test of interest, with all applicable severity grades displayed.

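### Laboratory results from an on-time post-treatment visit on days 31-33 fall outside the 30-day cut-off and cannot count as treatment-emergent abnormalities

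*SAP*

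**What the plan says.** **Timing of the visit.** Protocol 6.13 states: "All subjects must complete the PTx assessments 30 days after the last dose of study drug". Footnote a to the schedule in Protocol Appendix 2 agrees: "The Post-Treatment (PTx) visit should occur 30 days after the last dose of study drug". Subjects who enter the extension skip this visit. The visit-window row of that table, repeated in SAP Appendix 1, ends with ±3 days in the PTx position. Hematology, chemistry, vital signs and weight are all scheduled at PTx.

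**Cut-off for the summaries.**
- SAP 7, general rule: safety summaries "will include data collected up to the last dose of study drug plus 30 days".
- SAP 7.2, laboratory data: summaries are "for data collected up to the last dose of study drug plus 30 days for subjects who have permanently discontinued study drug".
- SAP 7.2.2.1, treatment-emergent laboratory abnormalities: counted "up to and including the date of last dose of study drug plus 30 days for subjects who permanently discontinued study drug". SAP 7.2.2.2 sets the same limit for marked abnormalities.
- SAP 7.2.2.3: "the denominator is the number of subjects with nonmissing postbaseline values up to 30 days after last dosing date".
- Protocol 8.6: safety data "up to 30 days after permanent discontinuation of study drug will be summarized by treatment group according to the study drug received".

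**Adverse events** are handled differently. SAP 7.1.5.1 classifies them by onset date, which must be "no later than 30 days after permanent discontinuation of study drug".

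**The concern.** The visit is targeted at the last day that the summaries accept. A subject who attends one to three days after the target is on time under the schedule, but the measurements taken that day are late under the SAP. Whether the result counts then depends on which side of day 30 the appointment fell.

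PTx is the only scheduled safety visit after the Week 24 or early termination visit for subjects who stay out of the extension. A new Grade 3 or 4 hematology or chemistry value first seen there on day 32 would not be treatment-emergent. Adverse event reporting would not reliably recover it, because Protocol 7.5 says that laboratory abnormalities are usually not recorded as adverse events.

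**Working it through.** **1. The PTx window.** The window row is blank for Screening and Day 1, then has nine entries: ±3, ±3, ±3, ±2, ±3, ±3, ±5, ±5, ±3. Eight belong to Weeks 2, 4, 6, 10, 14, 18, 20 and 24. The ninth, ±3, falls to PTx.

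**2. Permitted days against the cut-off.**
- Permitted days after last dose: 30 − 3 = 27 to 30 + 3 = 33, which is 33 − 27 + 1 = 7 days.
- Cut-off: day 30, inclusive.
- Days past the cut-off: 31, 32 and 33, so 3 of 7. As a share of permitted days, 3/7 = 43%.

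**3. Summaries that change for any subject with a PTx visit on those days.**
- Treatment-emergent and marked laboratory abnormalities (SAP 7.2.2.1, 7.2.2.2): the result cannot qualify.
- Denominator (SAP 7.2.2.3): the result does not count. The number itself changes only for a subject with no earlier post-baseline value for that test.
- Liver-test counts (SAP 7.2.3): no separate cut-off is given, so the limit in SAP 7 and 7.2 applies.

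**4. By-visit tables.** SAP Table 3-4 has no PTx visit. Records are assigned by study day, and SAP 3.7.3 selects the record closest to the nominal day. For PTx on days 31-33:

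| Last dose (study day) | PTx study days | Analysis window (Table 3-4) |
|---|---|---|
| 15 | 46-48 | Week 6 (37-57) |
| 29 | 60-62 | Week 10 (58-85) |
| 43 | 74-76 | Week 10 (58-85) |
| 71 | 102-104 | Week 14 (86-113) |
| 99 | 130-132 | Week 18 (114-141) |
| 127 | 158-160 | Week 24 (from 142) |
| 169 (completer) | 200-202 | Week 24 (from 142) |

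A completer with a Week 24 record near Day 169 would have that record selected anyway, so nothing changes. For an early discontinuer, the PTx record may be the only one, or the closest one, in a later window. The cut-off then removes laboratory and vital-sign values that a visit on day 30 or earlier could have supplied.

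**5. Weight of one subject.** With the planned arms of 15 and 30, one reclassified subject moves an incidence by 1/15 = 6.7 percentage points on placebo or 1/30 = 3.3 points on either filgotinib dose.

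**6. After the change.** With PTx assessments accepted to day 33, 0 of 7 permitted days fall outside the summaries.

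**The case against.** **The SAP follows the protocol.** Protocol 8.6 sets the same limit, adverse event collection also stops at 30 days, and a fixed 30-day period is a coherent choice. This stands as far as it goes: there is no conflict between SAP and protocol on the cut-off. The conflict is between that shared cut-off and the visit window, and both documents carry it. Protocol 7.3.2 provides for the early side of the window by keeping serious adverse events that occur after the follow-up visit but within 30 days of last dose. Nothing similar covers measurements on the late side.

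**The ±3 days for PTx stands only in a table row.** The text says simply 30 days. That is true, but the number and order of the entries fit no other reading.

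**Little is lost.** A reader might infer that the whole late visit is discarded. The documents do not support that:
- Adverse events with onset by day 30 count even if recorded on day 32, and all deaths observed are summarized.
- SAP 7.2 keeps every laboratory result in the by-subject listing, with abnormal values flagged. Only the narrower listing of treatment-emergent Grade 3 or 4 results depends on the cut-off.
- CRP is not affected. SAP 3.7.2 treats it as an inflammatory biomarker, and SAP 7.2.1 does not name it among the laboratory summaries.
- By-visit vital-sign and laboratory tables for completers with a Week 24 record do not change.
- Completers have Week 24 safety laboratory tests, and early leavers have them at early termination.

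All of this stands and limits the point to what is set out under steps 3 and 4 of the working.

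**A longer laboratory period creates its own mismatch.** An abnormal value on day 32 would be treatment-emergent while an adverse event starting that day would not. This is a real cost of the change.

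**Conclusion.** The mismatch is in the documents and rests only on reading ±3 days as the PTx window. For subjects who do not enter the extension, a compliant PTx visit on any of 3 of the 7 permitted days yields hematology and chemistry results that cannot count as treatment-emergent or marked abnormalities and are left out of the abnormality denominator and liver-test counts. Some early discontinuers also lose laboratory and vital-sign records from a later analysis window.

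A reader might take 3/7 to mean that 43% of PTx results are lost. That would require visits spread evenly over the window. The documents give no distribution of visit dates, and the true share could be anywhere from none to all. The number of subjects with a PTx visit is also unknown, out of about 75 planned.

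This is a minor point. It does not touch the efficacy analyses, and it is worth correcting because the correction is cheap and the arms are small.

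**What to change.** In SAP 7, 7.2, 7.2.2.1, 7.2.2.2 and 7.2.3, and in the denominator rule of 7.2.2.3, include assessments from the scheduled PTx visit made within its protocol window, that is, up to last dose + 33 days. Changing the definitions without the denominator would leave numerator and denominator covering different periods. Leave the 30-day onset rule for adverse events as it is.

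Because Protocol 8.6 states 30 days, record the departure in SAP 7.7, which now reports no deviations from the protocol-specified safety analyses. If the SAP is already final, record it in the clinical study report, as SAP Section 1 provides.

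The cost is a date or nominal-visit filter and a few sentences. The downsides are that abnormality counts may rise slightly and that the laboratory and adverse event periods will differ by up to 3 days.
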